4.1 Primary Endpoints and Assessment Methods

See Section 9.1 of the protocol.

As [Section 5.7](#) of the SAP Core Body, the following I16, I75 and I76 codes were not included in the primary objective/endpoint. This was also applicable for secondary objectives.

On the primary analysis, no exclusion of potential Covid-19 cases was conducted.

4.2 Secondary Endpoints and Assessment Methods

4.2.1 Effectiveness

See Section 9.2.1 of the protocol.

As described in [Section 5.7](#) of the SAP Core Body:

- the following I16, I75 and I76 codes were not included in the secondary objectives
- the MACE was not produced, but an analysis linked to MACE ICD-10 codes
- the flu peak period was not conducted as statistical analysis
- The panels from KELA were based on aggregated data

Based on HILMO data, no status on death was available. Death is reported through the eSAE panel. No formal cross analysis between HILMO and eSAE was conducted.

When analysis is based on "primary and secondary", the number of occurrences refers to the number of events with at least one diagnostic (either primary or secondary) compatible with the outcome definition.

4.2.2 Safety

See Section 9.2.2 of the protocol.

4.3 Observational Endpoints and Assessment Methods

See Section 3 of the protocol and [Section 4.2.1](#) of the SAP Core Body.

Regarding "Previous vaccinations during the last 5 years (administered product and date of vaccination)" as described in Section 5.2.6 of the protocol, data collected were restricted to flu and pneumonia vaccinations.

4.3.1 Safety

4.3.1.1 Codifications

eSAE were coded using MedDRA, and using primary SOC and PT. Codification was directly accessible via eSAE panel data. In addition, the ICD-10 codes were indicated at least for fatal eSAE.

For safety data from Finnish registers, the data were coded using a Finland ICD-10 codes (or occasionally ICPC-2 used in primary care registry). Each individual diagnosis code reported during the hospitalization is considered an individual SAE. The dictionary was the source to de-code with clear label using hierarchy ICD-10 methodology (used as hierarchy 0 to 2 or 3 in the statistical analysis).

For codification of ICPC-2, two files were available. A first file contained all possible ICPC-2 codes with the label of de-code. A second file select ICPC-2 codes linked to the primary objective, with a correspondence with an ICD-10 code. The list refers to ICPC-2 following selected codes:

- R (respiratory system): R72, R74 to R81, R83, R95 and R96
- K (circulatory system): K70, K74 to K80, K82, K84, K87 and K90 to K93.

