### ***Collection of safety data***

The SARs and AESIs, experienced by the subject and suspected to be related to the vaccine according to the HCP assessment, will be collected using an SAR/AESI paper form throughout the study (ie, from inclusion up to 31 August of the year following the vaccination). Additional data can be collected from the local medical patient file, as needed.

All other SAEs (non-fatal SAEs except those included in the primary endpoint) will be collected by THL from the Finnish health registers up to 6 months after vaccination. AESIs and fatal SAEs, which have not been reported by the HCPs, will be collected in the same manner throughout the study.

Note: AESIs include new onset of GBS, encephalitis / myelitis (including transverse myelitis), Bell's palsy, optic neuritis, and brachial neuritis.

Detailed description of the data reporting process from the HCPs to the Principal Investigator and from the Principal Investigator to Sanofi Pasteur is outlined in [Section 10](#).

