#### ***Serious Adverse Reaction (SAR) and suspected SAR:***

All noxious and unintended responses to the study vaccine related to any dose administered that results in death, is life-threatening, requires hospitalization or prolongation of existing

---

a The term "life-threatening" refers to an event in which the subject was at risk of death at the time of the event; it does not refer to an event which hypothetically might have caused death if it were more severe.

b All medical events leading to hospitalizations will be recorded and reported as SAEs, with the exception of: elective hospitalizations planned either before or after inclusion into the study or outpatient treatment with no hospitalization, or hospitalizations due to an AE defined in the primary endpoint.

c "Persistent or significant disability or incapacity" means that there is a substantial disruption of a person's ability to carry out normal life functions.

hospitalization, results in persistent or significant disability or incapacity, or is a congenital anomaly or birth defect.

A SAR refers to a potential causal relationship between the study vaccines and an SAE, based on the HCP assessment.

A suspected SAR refers to individual SAR cases reported by the HCPs where a causal relationship between the SAE and the study vaccines is suspected by either the Principal Investigator or the Sponsor.

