### **10.6 Reporting of Cardiovascular and Respiratory Events**

Cardiovascular and respiratory effectiveness endpoints as specified in this protocol will not be considered as SAEs and are waived from regulatory reporting to health authorities except if the Principal Investigator according to his/her best medical judgment considers these events as endpoint-related SARs. In that case, the Principal Investigator or delegate sub-Investigators must report the endpoint-related SAR within 24 hours after the awareness of any THL study personnel to the Sponsor’s GPV Department, the CRA, and the CTL using an SAE eCRF in the EDC system. The Sponsor will inform the relevant health authorities of the endpoint-related SAR according to local regulatory requirements.

In addition, the Sponsor will provide summaries of endpoint-related SAR on a quarterly basis to the relevant health authorities.

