3.2 Study Plan

Randomization and Vaccination

All eligible subjects were randomized to receive a single IM injection of either QIV-HD or QIV-SD at Day 0. A scratchable list was used to randomly assign subjects to either the QIV-HD group or the QIV-SD group. All subjects were observed for 20 minutes after vaccination to ensure their safety.

Recording of Data

Finland uses multiple registers to collect different health and population data. Subject data were recorded in the local medical patient file by health care professionals (HCPs). From patient files the data was transferred automatically to the corresponding Finnish health registers (hospital diagnosis/treatment and SAEs).

Collection of Datasets

The datasets were collected using multiple Finnish health registers and compiled by THL into an analysis database. The subject's Personal Identity Code (PIC) constituted the common key between all of the registers. On a regular basis, THL extracted the study data from the different Finnish registers and when required from local medical patient files. THL submitted protocol-defined datasets to Sanofi Pasteur in a pseudonymised manner (ie, PIC will not be transferred to Sanofi Pasteur to maintain data privacy).

Collection of safety data

Serious adverse reactions (SARs) and AESIs, experienced by the subject and suspected to be related to the vaccine according to the HCP assessment, were collected using an SAR/AESI paper form throughout the study (ie, from inclusion up to 31 August of the year following the vaccination). All fatal SAEs, irrespective of causality, were collected for the same period using real-time surveillance of population data. Additional data could be collected from the local medical patient file, as needed.

All SAEs resulting in hospitalization were collected by THL from the Finnish health registers up to 6 months after vaccination. AESIs, which had not been reported by the HCPs, were collected from the Finnish health registers up to 6 months after vaccination, and reported as eSAE.

Note: AESIs included new onset of Guillain-Barré syndrome (GBS), encephalitis / myelitis (including transverse myelitis), Bell's palsy, optic neuritis, and brachial neuritis.

4 Endpoints and Assessment Methods

See Section 9 of the protocol.

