No analysis is anticipated linked to Social Welfare registry identified in the Table 11.1 of the protocol. Of note: No specific links objectives/endpoints are mentioned for these data in the protocol.

Additionally, in safety endpoint, we have in the protocol: "Occurrence and nature (MedDRA PT or ICD-10 codes) of non-fatal SAEs by time to onset and seriousness criteria up to 6 months after vaccination". Nevertheless, information around hospitalizations (from HILMO) don't include the

fatality. The hospitalization analysis (all SAE) will be conducted without considering fatality (non-fatal or fatal). Secondly, the seriousness analysis is based only on eSAE, as not available in all hospitalizations via HILMO registry.

Of note:

- Due to the context of the study no Adjudication Review Committee (ARC) was put in place. It was a possibility identified in the protocol to review primary outcomes.
- During the 2019-2020, no anti-influenza medications were observed in the study cohort. Therefore, only antibacterial data are present in thl_med.
- Regarding "Previous vaccinations during the last 5 years (administered product and date of vaccination)" as described in Section 5.2.6 of the protocol, data collected were restricted to flu and pneumonia vaccinations.
- For the 3 panels referring to aggregated data, a first run will be done without considering the intervention group. When unblind is managed, THL will generate a second run, in order to obtain dataset taking into account injected group information, i.e. aggregation by treatment group.

6 References List

- 1 Newcombe R.G., Two-sided confidence intervals for the single proportion: comparison of seven methods, *Statistics in Medicine*, (1998) 17, 857-872

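### SAP 4.3.1.1 makes every diagnosis code of a hospital stay a separate SAE, whereas the protocol's SAE is the event that led to or prolonged the stay; SAP 5.7 does not record the change

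*SAP*

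**What the plan says.** **SAP counting rule.** SAP 4.3.1.1, on safety data from the Finnish registers: "Each individual diagnosis code reported during the hospitalization is considered an individual SAE". Nothing limits this to the primary, causative or new diagnosis. SAP 4.3.1.2 takes the admission date as onset of a HILMO SAE, and 4.3.1.3 takes the length of stay as its duration. SAP 4.2.1 shows that the hospital data hold secondary as well as primary diagnoses.

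**Protocol definition.** Protocol 9.2.2.1 includes as SAEs events that require inpatient hospitalization or prolong an existing one. Footnote b gives the unit and the first exclusion: "All medical events leading to hospitalizations will be recorded and reported as SAEs, with the exception of: elective hospitalizations planned" (before or after inclusion). The same footnote also excludes outpatient treatment and gives the other exclusion that matters here: "or hospitalizations due to an AE defined in the primary endpoint". Protocol 10.6 repeats that the cardiovascular and respiratory endpoints "will not be considered as SAEs and are waived from regulatory reporting to health authorities", unless the investigator judges one to be an endpoint-related SAR. Protocol 5.1.3 carries the exception into data collection: "All other SAEs (non-fatal SAEs except those included in the primary endpoint) will be collected by THL from the Finnish health registers".

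**SAP on scope.** SAP 4.2.2 refers back to protocol 9.2.2. SAP 3.2 says: "All SAEs resulting in hospitalization were collected by THL from the Finnish health registers up to 6 months after vaccination", without the primary-endpoint exception. SAP 5.7 labels the hospitalization analysis as one of all SAEs, with fatal and non-fatal pooled. It explains the changes on fatality and seriousness. It mentions neither the one-code rule nor the two exclusions.

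**The concern.** A chronic disease recorded as a secondary diagnosis usually did not cause the stay and did not begin on the day of admission. Under the SAP rule it is tabulated as an SAE that starts that day and lasts as long as the stay. Diabetes of many years' standing, coded at an admission on day 40, becomes an SAE with onset on day 40.

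This matters because protocol 9.2.2.3.2 says that non-fatal register SAEs are not individually assessed for causality. For ordinary hospitalizations the frequency tables are the evidence, and no case review removes the comorbidity codes. In a population aged 65 and over, rows for common chronic conditions could consist largely of background coding, and a difference in new events between the groups would be harder to see.

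The SAP is also not consistent with itself. For effectiveness outcomes on primary and secondary diagnoses, 4.2.1 counts events with at least one compatible diagnosis. Only the safety rule counts codes.

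**Working it through.** No figure in the plan tests this point. The check is a comparison of text, followed by illustrations on stated assumptions.

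**1. Text comparison**

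| Item | Protocol | SAP |
|---|---|---|
| Unit | Event leading to or prolonging the stay (9.2.2.1) | Each diagnosis code (4.3.1.1) |
| Onset | Time to onset of the SAE (9.2.2.2) | Admission date for every code (4.3.1.2) |
| Elective stays | Excluded (9.2.2.1, footnote b) | No filter written; 4.2.2 refers to protocol 9.2.2 |
| Primary-endpoint stays | Excluded (footnote b, 5.1.3, 10.6) | Exception absent from 3.2; 5.7 speaks of all SAEs; 4.2.2 refers to protocol 9.2.2 |
| Recorded as a change | n/a | Not in 5.7 |

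The first two rows are departures in written text. The next two are unclear.

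**2. Event counts.** With k codes per stay, S stays give k × S SAEs. The documents do not give k. Assuming k = 2, 3 or 5, 1000 stays give 2000, 3000 or 5000 SAEs. The count of subjects with at least one SAE is the same for every k, because the first code already makes the subject a case.

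**3. Dilution of a ratio.** Let incident records for a code be 1 in one group and 2 in the other, with b background records added to each. The observed ratio is (2 + b)/(1 + b):
- b = 1: 3/2 = 1.5
- b = 2: 4/3 = 1.33
- b = 4: 6/5 = 1.2

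**4. Per-code subject percentages.** SAP 3.1 gives 33 093 vaccinated subjects, so about 16 546 per group. Assume new-onset rates of 0.2% and 0.4%, and comorbidity coding that adds the same percentage to both groups without overlap. The difference stays at 0.2 percentage points. Its standard error is √[(p₁(1−p₁) + p₂(1−p₂))/16 546].

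| Background added | Observed rates | Ratio | SE of difference (points) | Power, two-sided 5% |
|---|---|---|---|---|
| 0 | 0.2% vs 0.4% | 2.00 | 0.060 | 91% |
| 0.5% | 0.7% vs 0.9% | 1.29 | 0.098 | 53% |
| 2% | 2.2% vs 2.4% | 1.09 | 0.165 | 23% |

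No such test is planned. Power serves here only as a measure of how far the contrast is blurred.

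**5. Primary-endpoint stays, if they were not filtered out.** SAP 5.5 gives about 450 cases, and 450/33 093 = 1.36% of subjects. This is approximate because the windows differ. Injections ran from 4 November to 23 December 2019 (SAP 4.3.3.3), so six months ends between 4 May and 23 June 2020. The endpoint window runs from day 14 to 31 May.

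**The case against.** **On the counting rule.** Over-inclusive counting can be defended as cautious in a descriptive safety analysis, and protocol 9.2.2.2 allows the nature of an SAE to be given by ICD-10 code. The safety summaries with confidence intervals are per subject (SAP 5.1.2.2), randomization balances the background on average, and absolute differences are unbiased. All of that is right, and it protects the any-SAE percentage. It does not protect the number of events, which SAP Table 5.1 also plans to show, nor the per-code percentages, onset classes and durations. Describing an SAE by its code is also different from making each code an SAE.

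**On primary diagnosis as a remedy.** A new event that prolongs a stay is an SAE under protocol 9.2.2.1 and may be recorded only as a secondary code. A table of primary diagnoses alone would lose it. This objection stands, and it is why the all-codes table has to be kept.

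**Stronger readings that the documents do not support.**
- A reader might infer that elective and primary-endpoint stays are in fact counted as SAEs. The SAP does not say so. It refers back to protocol 9.2.2, and the Data Transfer Agreement, which might restrict the hospitalization panel, is not available. The gap is that the handling is not stated.
- A reader might infer harm to signal detection. That is a separate blinded process during the study, comparing frequencies with a register baseline (protocol 10.1). The SAP does not say that it uses this rule, and coding both sides alike would have a different effect.
- A reader might take these tables to be the only safety analysis of non-fatal SAEs. Non-fatal SARs and AESIs are analysed from the eSAE panel (SAP 4.3.1.4), as are reports suspected by a health care professional but judged unrelated by the investigator.
- A reader might fear that a benefit on endpoint stays could offset an excess elsewhere. Register data are shown by ICD-10 hierarchy, so circulatory and respiratory codes have their own rows.

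**Conclusion.** The point holds as a departure in written text. SAP 4.3.1.1 replaces the protocol's event-based SAE with a code-based one, dates every code from admission, and does not record this in 5.7. Event counts rise in proportion to the codes per stay. Per-code subject percentages rise with comorbidity coding, and ratios between the groups shrink towards 1. The any-SAE subject count is not affected by the number of codes.

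The size cannot be fixed from the documents. The ratios of 1.5, 1.33 and 1.2 rest on assumed background multiples of 1, 2 and 4, and the power figures on assumed rates. They show direction and plausible scale only.

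The second part is a gap: the SAP does not state how elective and primary-endpoint stays are handled. If endpoint stays were left in, about 1.4% of subjects could enter the SAE numerator through them. Neither part affects the primary effectiveness analysis.

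**What to change.** 1. Replace the one-code-one-SAE rule for the main register SAE table. Count unscheduled stays within 6 months of vaccination, by stay, coded by primary discharge diagnosis.
2. Show stays with a primary-endpoint code from day 14 to 31 May in a separate block outside the SAE total. Endpoint events judged to be SARs continue to be reported through the eSAE panel.
3. Keep the all-codes table beside it, labelled as including comorbidities, so that in-hospital events recorded only as secondary codes, including possible prolongation SAEs, remain visible.
4. Record in SAP 5.7 the counting rule and the handling of both exclusions.

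The cost is SAP wording and one re-run table. Protocol Table 11.1 lists type of admission among the HILMO fields, the primary endpoint already needs unscheduled stays to be identified, and SAP 4.2.1 already separates primary from secondary diagnoses. The downside is that events coded only as secondary diagnoses appear only in the all-codes table.

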4.3.1.2 Time to Onset

Time to onset is defined as:

- Start date of the eSAE minus vaccination date
- Admission date for SAE from HILMO minus vaccination date
- Visit date for hospital emergency room visits or primary care visits to physician minus vaccination date

The class of analysis for presentation is:

- Missing onset
- 0 to 13 days
- 14 to 30 days
- 31 to 60 days
- 61 to 90 days
- 91 to 120 days
- 121 days and above

4.3.1.3 Duration

Duration of an eSAE is defined as stop date minus start date plus 1.

Duration of an SAE from HILMO is defined as discharge date minus admission date plus 1.

The duration is not applicable for hospital emergency room visits or primary care visits to physician.

The class of analysis for presentation is:

- Missing duration
- 1 to 3 days
- 4 to 7 days
- 8 to 14 days
- 15 to 28 days
- 29 days and above

4.3.1.4 Nature of the eSAE

eSAE refers to at least one of the following classes: SAR, AESI or fatal. It's an extraction of pharmacovigilance database and keeping key variables.

In addition, potentially related SAE (eg, in paper form) by any HCP but assessed as unrelated by the investigator are presented. Therefore, such eSAE are considered as "Other eSAE" in the statistical analysis.

4.3.1.5 Causal Relationship for eSAE

The relationship is the final investigator assessment, and refers to Yes/Related or No/Not related. If Yes, the eSAE is a SAR.

4.3.2 Derived Other Variables

4.3.2.1 Seriousness for eSAE

Seriousness was collected (and analyzed) for eSAE using the following modalities:

- Congenital Anomaly
- Significant Disability
- Death
- Hospitalized
- Life Threatening
- Medically Significant
- Missing seriousness (modality for analysis)

Modalities were not mutually exclusive.

4.3.2.2 Outcome for eSAE

Outcome were collected (and analyzed) for eSAE using the following modalities:

- Fatal
- Not recovered / Not resolved
- Recovered / Resolved
- Recovered / Resolved with sequelae
- Recovering / Resolving
- Unknown

4.3.3 Derived Other Variables

4.3.3.1 Age for Demographics

The age (in full years, expressed as an integer) corresponds to the age at the time of injection.

Some analyses are done using predefined age groups (eg, 65-74y vs 75y and above, or focus on 85y and above).

4.3.3.2 Other Baseline Characteristics

The following baseline data are also collected: sex, flu and pneumonia vaccines in the last 5 years, comorbidities (in 5 different factors), and baseline care allowance status.

The variables are used as they are or identified such as: "at least one".

4.3.3.3 Durations of a Subject in the Trial

The date of injection corresponds to the start date of the subject. The ICF date is also available for information in the individual data appendix. All subjects were injected between 04NOV2019 and 23DEC2019.

For key duration computations, the start date is the vaccination plus 14 days.

The final date corresponds to:

- 31AUG2020 or 31MAY2020, depending on analysis
or
- Censoring occurs at the following situations:
 - When a case occurs (for rVE analysis and Kaplan-Meier [KM] figure), date of the event
 - When withdrawal of consent, date of withdrawal of consent
 - When death (using eSAE data), date of death

The duration is the 'final date' minus 'start date' plus 1.

The minimum is 1 day, and the maximum is 302 days (31AUG2020-04NOV2019+1).

The duration is also used for person-year computations (1 year = 365.25 days).

5 Statistical Methods and Determination of Sample Size

The statistical analyses for the study report will be performed under the responsibility of the Sponsor's Biostatistics platform using SAS®.

The SAP v1 is approved before the official final database and before the unblinding steps.

Post-hoc additional exploratory analyses may also occur in later step (eg, deeper sub-analyses, or eventually explore additional data after amendment of the DTA).

The database is locked before unblinding the subjects.

For descriptive purposes, the following statistics will be presented:

Table 5.1: Key descriptive statistics produced

Baseline characteristics and follow-up description	Categorical data	Number of subjects. Percentage of subjects.
	Continuous data	Mean, standard deviation, quartiles, minimum, and maximum.
Effectiveness results	Categorical data	Number and percentage (95% CIs) of subjects. Number of occurrences, rVE and 95% CIs.
Safety events	Categorical data	Number and percentage (95% CIs) of subjects, and number of events.

The Confidence Interval (CI) for the single proportion will be calculated using the exact binomial method (Clopper-Pearson method, quoted by Newcombe).

For the percentage in the tables, two decimals will be kept, except in the following cases:

- If numerator is 0, then the value of percentage will be presented as “0” (no decimal).
- Else if numerator is >0 and numerator = denominator, then the value of percentage will be presented as “100” (no decimal).
- Else if numerator is >0 and the directly calculated percentage is <0.01, the value of percentage will not be presented as “0.00” but will be presented as “<0.01”.
- Else if the frequencies of numerator and denominator are both >0 and numerator does not equal to denominator, and the directly calculated percentage is >99.99, the value of percentage will not be presented as “100.00” but will be presented as “>99.99”.

The description of the database is presented in [Section 4](#).

